## 4.2.3 Sensitivity Analysis

For the sensitivity analysis, a multiple imputation with 100 repetitions will be performed to receive the responder criterium for participants with missing DRSS assessment on Visit 15 (week 48) due to early discontinuation (*hypothetical strategy*). The imputation model used to generate complete data sets will be a logistic regression for the responder criterium with stratum (baseline DRSS) and treatment group as effects. To use the regression method, the pattern of missingness need to be monotone.

Participants who had a VTC in the study eye prior to the missing assessment will be considered non-responders regardless of the DRSS level (*composite variable strategy*).

Treatment groups will be runcaciguat and placebo, actually administered dose levels will not be considered for this analysis.

The analyses will be performed on the PPS and will include only study intervention compliant participants (*principal stratum strategy*).

The analysis using Bayesian inference with non-informative priors, as described in the section above, will be repeated on the complete data sets obtained from the multiple imputation.

### 4.2.4 Subgroup Analyses

To build hypothesis on subpopulations with better treatment response and on parameters that may be useful as biomarkers for activity, the following subgroups may be assessed if of relevant size (at least 10 participants per arm), as the underlying characteristics may influence the primary efficacy endpoint:

DRSS at baseline

- 47
- 53

Sex

- Male
- Female

Diabetes

- Type 1
- Type 2

Age

- $\geq$  median age
- < median age

Hypertension at baseline

- Yes (SBP  $\ge$  140 mmHg and/or DBP  $\ge$  90 mmHg)
- No (SBP < 140 mmHg and DBP < 90 mmHg)

Version 3.0

Decrease in DBP (Visit 6 vs. Baseline)

- Yes: decrease  $\geq$  5 mmHg
- Yes: decrease  $\geq 10 \text{ mmHg}$
- No

HbA1c at baseline

- ≤ 8.5%
- > 8.5%

Renal function at baseline by eGFR

- $eGFR \le 60 \text{ mL/min}$
- eGFR  $\leq$  45 mL/min (only if  $\geq$  10 participants)

The primary analysis will be repeated by subgroups as defined above. This way it is possible to assess the treatment effect on DRSS improvement within subgroups. The analyses of subgroups will be performed on the PPS.

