9.4.2 Primary endpoint

The primary endpoint is "≥ 2-step improvement in DRSS at 48 weeks of treatment in the study eye".

Missing data for this endpoint will be imputed using the last measured DRSS score prior to this

If the last measured DRSS score already showed an improvement by ≥ 2 steps at the last measurement prior to the missing assessment, the participant will be considered a responder for the primary endpoint. Otherwise, the participant will be considered a non-responder.

Participants that had a vision-threatening complication as defined in Section 8.1.2 prior to the missing assessment will be considered non-responders.

The primary analysis will be conducted using a Bayesian framework. This decision depends upon the following criteria:

- (a) there is \geq 90% posterior probability for superiority vs placebo and
- (b) if there is \geq 50% posterior probability that the proportion of patients with DRSS \geq 2-step improvement exceeds 25%.

The response criterion is assumed to be binomially distributed within each treatment arm. For the Bayesian evaluation, a Jeffries' prior (i.e. a Beta (0.5;0.5)-prior) will be used. Under these assumptions, the posterior distribution for the parameter π will be a Beta (k+0.5,n-k+0.5)-distribution, where

- k is the number of patients with DRSS \geq 2step improvement within the respective study arm and
- n is the number of participants within the respective study arms.

In order to demonstrate criterion (a), the posterior distribution of $\pi_{ACT} - \pi_{PLC}$ will be used to establish the posterior probability that $\pi_{ACT} - \pi_{PLC} > 0$ (e.g. by using a Monte-Carloapproach).

The posterior distribution for criterion (b) can be directly evaluated from the Beta (k+0.5,n-k+0.5)- distribution in the runcaciguat arm.

This primary analysis will be conducted on the PPS. A sensitivity analysis will be performed on the FAS. Further sensitivity analyses will include a separate analysis for each runcaciguat dose level that was reached during titration (on the PPS), as well as an analysis in the subpopulation of participants without major changes in vital signs (i.e. systolic blood pressure and pulse rate). Another sensitivity analysis will be conducted using multiple imputations for missing data. This analysis will be described in the SAP in a more detailed way.

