## 4.2.2 Main Analytical Approach

For the primary analysis, the last observation before missing DRSS values will be carried forward (LOCF) to impute missing values if the participant dropped out after visit 9 (week 12) and the EoT DRSS assessment was performed within 4 weeks of treatment discontinuation (*while on treatment strategy*). If the last measured DRSS score already showed an improvement by  $\geq 2$  steps at the last measurement prior to the missing assessment, the participant will be considered a responder for the primary endpoint. Otherwise, the participant will be considered a non-responder. If the participant dropped out after visit 9 (week 12) and the EoT DRSS assessment was performed more than 4 weeks after treatment discontinuation the last available DRSS assessment prior to treatment discontinuation will be used (LOCF) (*while on treatment strategy*). Participants who dropped out before visit 9 (week 12), or who had a VTC in the study eye prior to the missing assessment will be considered non-responders regardless of the DRSS level (*composite variable strategy*).

Treatment groups will be runcaciguat and placebo, actually administered dose levels will not be considered for this analysis.

Primary efficacy analyses will be performed on the PPS and will include only study intervention compliant participants (*principal stratum strategy*). In addition, sensitivity analyses will be performed on the FAS. Further analyses may include a separate analysis for each runcaciguat maintenance dose level that was reached during titration (on the PPS). Participants will be analyzed according to the treatment (i.e., runcaciguat or placebo) they actually received.

The study will be analyzed using Bayesian inference with non-informative priors. PoC shall be defined as fulfillment of the following criteria:

•  $P(\pi_{ACT} - \pi_{PLC} > 0 | data) \ge 0.9$ i.e., the posterior probability that the difference between  $\pi_{ACT}$  and  $\pi_{PLC}$  is greater than 0 (clinical activity) given the data observed in the study needs to be 90% or more,

and

•  $P(\pi_{ACT} > 0.25 | data) \ge 0.5$ i.e., the posterior probability that  $\pi_{ACT}$  is greater than 0.25 (clinical relevance) given the data observed in the study needs to be 50% or more.

95% credible intervals will also be presented for  $\pi_{ACT}$  and for  $\pi_{PLC}$ 

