#### 4.5.1 Treatment Compliance, Duration and Exposure

Tables will be presented for the FAS and PPS.

Frequency tables and summary statistics will be presented for total dose, treatment dose per week, and treatment duration (absolute duration and frequencies with weekly intervals). In addition, treatment compliance will be summarized presenting the percent of tablets that were actually taken out of the planned number of tablets. Frequencies of participants showing compliance <80%, 80-120%, and >120% of the planned tablets will be presented.

The frequencies of dose modifications will be presented by treatment group and visit, especially to assess the escalation, maintenance, reduction, and withdrawal of doses, including the reasons for maintenance, reduction, or withdrawal. Furthermore, the frequency of participants being treated on a certain dose level will be presented by treatment group, visit and dose level to assess the titration level being reached during up-titration and in the maintenance phase.

A listing with the actual dose levels or sham-titration levels for each visit will be presented to get an overview of the individual titration schemes.

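### SAP 4.2.4 repeats the randomised arm comparison in subgroups defined by the fall in diastolic pressure at Visit 6, which the drug itself changes, so the result is not a treatment effect

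*SAP*

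**What the plan says.** SAP 4.2.4 gives a list introduced by "the following subgroups may be assessed if of relevant size (at least 10 participants per arm". Every entry is fixed before treatment (baseline DRSS, sex, diabetes type, age, baseline hypertension, baseline HbA1c, baseline eGFR) except one: "Decrease in DBP (Visit 6 vs. Baseline", with categories for a fall of at least 5 mmHg, a fall of at least 10 mmHg, and no. The section then states that the primary analysis is repeated in these subgroups on the per-protocol set, and adds: "This way it is possible to assess the treatment effect on DRSS improvement within subgroups". The stated aim is to build hypotheses.

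The protocol schedule of activities puts Visit 6 at day 29, one week after the last titration decision. Protocol Table 2-1 gives a placebo-corrected DBP change of -4.0 mmHg at 90 mg (90% CI -7.2 to -0.8).

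A related analysis groups participants by dose reached. Protocol 9.4.2 is firm: "Further sensitivity analyses will include a separate analysis for each runcaciguat dose level that was reached during titration (on the PPS". SAP 4.2.2 makes it optional: "Further analyses may include a separate analysis for each runcaciguat maintenance dose level that was reached during titration (on the PPS". Neither names the placebo comparator for DRSS. Protocol 9.4.2 also plans, in the same sentence, "as well as an analysis in the subpopulation of participants without major changes in vital signs"; this does not reappear in SAP 4.2, and SAP 4.8 does not list its removal.

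**The concern.** A subgroup gives a treatment effect only if membership does not depend on treatment. A fall in DBP by day 29 is partly an outcome of treatment. A placebo participant whose DBP falls by 5 mmHg does so unaided; some runcaciguat participants in the same category are there only because of the drug. If anything that drives DBP change also bears on DRSS response, the two arms within the category differ in prognosis, and the repeated primary analysis mixes that difference with any drug effect. Neither document warns of this.

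The dose level reached has the same nature: under protocol 6.5.1 it is decided by systolic pressure and tolerability on treatment.

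What is at stake is interpretation. SAP 4.2.4 says the subgroups are meant to suggest who responds better and which parameters may serve as markers of activity, and a distorted comparison is a poor source for either.

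**Working it through.** **The rule being repeated.** The plan gives no figure for these subgroups. Its own figure for the primary rule reproduces: exact enumeration with Beta(0.5, 0.5) priors, 40 per arm and true rates 10% and 35% gives 90.3% probability of meeting both criteria, against the stated 90% or more.

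**Who enters the category of at least 5 mmHg.**

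Inputs: drug effect d = 4.0 mmHg (protocol Table 2-1, 90 mg, healthy participants, 7 days); SD of DBP change s = 8 or 10 mmHg (assumed; not in the documents); no mean change on placebo (assumed).

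Share = 1 - Φ((5 - d)/s).

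- s = 8: runcaciguat 1 - Φ(0.125) = 45.0%; placebo 1 - Φ(0.625) = 26.6%.
- s = 10: runcaciguat 1 - Φ(0.10) = 46.0%; placebo 1 - Φ(0.50) = 30.9%.
- Across the confidence limits (d = 0.8 to 7.2) at s = 10: runcaciguat 34% to 59%, placebo still 31%.

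With 40 evaluable per arm and s = 10 that is about 18 against 12 participants. The placebo group reaches the required 10 in 83% of trials (65% at s = 8), so this category would probably be analysed. For a fall of at least 10 mmHg it does so in only 9% (1% at s = 8).

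**Bias when the drug does nothing to DRSS.** Assume a standard normal prognostic factor u, correlated 0.5 with DBP fall and ρ with a normal response liability whose upper 10% are responders (the plan's placebo rate). With X the liability and Y the standardised fall, correlated 0.5ρ,

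P(response | fall ≥ 5) = P(X > 1.2816, Y > (5 - d)/s) / P(Y > (5 - d)/s).

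Results for s = 10 (differences taken before rounding):

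| ρ (assumed) | Drug effect on DBP | Runcaciguat % | Placebo % | Difference, points |
|---|---|---|---|---|
| 0 | 4.0 in all | 10.00 | 10.00 | 0 |
| +0.3 | 4.0 in all | 12.29 | 13.14 | -0.86 |
| +0.5 | 4.0 in all | 13.82 | 15.39 | -1.57 |
| +0.3 | 8.0 if u < 0, otherwise 0 | 10.89 | 13.14 | -2.25 |
| +0.5 | 8.0 if u < 0, otherwise 0 | 11.56 | 15.39 | -3.83 |
| -0.3 | 4.0 in all | 7.76 | 7.15 | +0.61 |
| -0.5 | 4.0 in all | 6.30 | 5.43 | +0.88 |

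At s = 8 the four rows with positive ρ become -1.10, -2.03, -2.92 and -4.99. At d = 0.8 with s = 10 the uniform-effect bias shrinks to -0.18 and -0.34.

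**Against sampling error.** With 18 and 12 participants at 10% response, SE = √(0.1 × 0.9 × (1/18 + 1/12)) = 11.2 points. With no bias, the 0.9 activity criterion is met falsely 8.6% of the time in such a subgroup; with 13.8% against 15.4% it is 9.1%, and with 11.6% against 15.4% it is 6.2%.

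**Dose level reached.** Under the same kind of model, assume 50% to 70% reach 120 mg and the factor correlates 0.3 to 0.5 with tolerating it (ρ = 0.3 to 0.5). Response is then 10.8% to 13.5% at the top dose and 5.4% to 8.7% below it, although the drug has no effect: an apparent dose-response made by selection.

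**The case against.** The best defence is that these analyses carry little weight. They are hypothesis-building, optional in the SAP and subject to a minimum size, and no subgroup enters the proof-of-concept rule. The likely bias is far smaller than the sampling error. This stands as a limit on importance. It does not rescue the sentence that the comparison assesses the treatment effect, because hypothesis-building status does not make the arms comparable.

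Several stronger readings are tempting and are not supported.

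- *The dose-level analysis compares each dose with all placebo.* A reader might infer this because protocol 9.4.1 (summary statistics) and SAP 4.5.2 (adverse events) pool placebo. For DRSS the comparator is simply not named.
- *These analyses will set the dose and biomarkers for the next compound.* Protocol 2.1 gives the study that purpose, but points to the PK/PD work in Part 1; protocol 8.4 plans exposure-response models separately, and SAP 4.6.3 has its own responder analysis within the runcaciguat arm.
- *The DBP subgroup will manufacture a benefit.* With a positive correlation the bias runs against the drug; with a negative one it favours it. Nothing in the documents fixes the sign.
- *The overlapping cut-offs of 5 and 10 mmHg are an error.* They are nested thresholds, like eGFR 60 and 45 in the same list: a matter of presentation.
- *Matching on sham-titration level solves the dose-level problem.* SAP 4.5.1 does provide for it: "A listing with the actual dose levels or sham-titration levels for each visit will be presented". But sham level is also reached after randomisation, and tolerating sham is not tolerating the drug.

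**Conclusion.** The point holds for the DBP-fall subgroup: the variable is measured after titration, the protocol's own data show that the drug moves it, and the SAP claims a treatment effect within its categories without a caveat. The imbalance in who enters the category of at least 5 mmHg is about 45-46% against 27-31%, given a 4.0 mmHg effect carried over from healthy participants and an assumed SD of 8 to 10. The resulting bias in response rate is roughly 1 to 2 points under a uniform effect on DBP and a positive link, and up to about 4 at SD 10 (5 at SD 8) if the fall is confined to some participants. It is zero if no factor drives both DBP change and DRSS response. All the correlations are assumptions.

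The analysis by dose level reached needs the same caution, but its comparator is unstated, so no bias against placebo can be assigned to it. The sample size and the proof-of-concept decision are untouched. This is a minor but clear correction.

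**What to change.** In SAP 4.2.4, remove the DBP-fall categories from the subgroups in which the arm comparison is repeated and put baseline DBP in their place; the baseline hypertension subgroup already covers similar ground. Report DBP change to Visit 6 against DRSS change within the runcaciguat arm as descriptive pharmacodynamics, noting that this association is also open to a shared prognostic factor.

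In SAP 4.2.2, name the comparator for the analysis by dose level reached, label the analysis descriptive and non-randomised, and omit the proof-of-concept posterior probabilities. Placebo participants at the same sham-titration level may be shown alongside, with a note that this does not by itself restore comparability. Apply the same label to the protocol's analysis of participants without major vital-sign changes if it is run, or record its removal in SAP 4.8.

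The cost is SAP wording before unmasking: no new data and no change in sample size. What is lost is a between-arm contrast by DBP response that could not be read as a treatment effect.

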The response criterion is assumed to be binomially distributed within each treatment arm. For the Bayesian evaluation, a Jeffrey's prior (i.e., a Beta (0.5,0.5)-prior) will be used. Under these assumptions, the posterior distribution for the parameter  $\pi$  will be a Beta (k+0.5, n-k+0.5)-distribution, where

- k is the number of patients with DRSS  $\geq$  2-step improvement within the respective study arm and
- n is the number of patients within the respective study arms.

In order to demonstrate the clinical activity, the posterior distribution of  $\pi_{ACT} - \pi_{PLC}$  will be used to establish the posterior probability that  $\pi_{ACT} - \pi_{PLC} > 0$  by using a Monte-Carlo-approach.

The posterior distribution for clinical relevance can be directly evaluated from the Beta (k+0.5, n-k+0.5)-distribution in the runcaciguat arm.

The Bayesian posterior probabilities  $P(\pi_{ACT} - \pi_{PLC} > 0 | data)$  and  $P(\pi_{ACT} > 0.25 | data)$  will be calculated using a Monte Carlo Approach: Within each arm, 100000 samples will be obtained from the posterior distribution (i.e., a Beta (k+0.5, n-k+0.5)-distribution). As a seed for random number generation, a fixed seed will be used. This seed has to be included into the program output, in order to ensure that the analysis can be repeated.

From these random samples, the following quantities will be obtained:

- Estimation of  $P(\pi_{ACT} \pi_{PLC} > 0 | data)$ :
  - Difference  $\delta^{(i)}$  between the ith sampled proportion in the active arm  $(=\pi_{ACT}^{(i)})$  and the ith sampled proportion in the placebo arm  $(=\pi_{PLC}^{(i)})$ :  $\delta^{(i)} = \pi_{ACT}^{(i)} - \pi_{PLC}^{(i)}$
  - Relative frequency of the event ' $\delta^{(i)} > 0$ ' within the samples of  $\delta^{(i)}$
- Estimation of  $P(\pi_{ACT} > 0.25 | data)$ :
  - Relative frequency of the event ' $\pi_{ACT}^{(i)} > 0.25$ ' within the samples of  $\pi_{ACT}^{(i)}$

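### SAP 4.2.4 looks for subpopulations that respond better but specifies no comparison between subgroups, and lists no eGFR > 60 group to compare with eGFR ≤ 60

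*SAP*

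**What the plan says.** SAP 4.2.4 lists eight factors. Six are baseline factors with two complementary levels: DRSS level, sex, diabetes type, age at the median, hypertension and HbA1c. Renal function has eGFR ≤ 60 and, nested inside it, eGFR ≤ 45; no group above 60 is listed. The eighth factor, fall in diastolic pressure at Visit 6, is measured after randomisation and has overlapping levels, so it is left out of this point.

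The purpose is "To build hypothesis on subpopulations with better treatment response and on parameters that may be useful as biomarkers for activity". The analyses are conditional on size: "subgroups may be assessed if of relevant size (at least 10 participants per arm" is the rule. The method is "The primary analysis will be repeated by subgroups as defined above", on the per-protocol set, and the SAP describes what this delivers: "This way it is possible to assess the treatment effect on DRSS improvement within subgroups".

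The analysis being repeated is in SAP 4.2.2. It has two criteria. The posterior probability that the runcaciguat response rate exceeds placebo, "given the data observed in the study needs to be 90% or more"; the posterior probability that the runcaciguat rate exceeds 0.25, "given the data observed in the study needs to be 50% or more". It uses a Beta(0.5, 0.5) prior in each arm and also presents a 95% credible interval for each arm's rate. SAP 4.2.5 adds descriptive DRSS statistics by the same subgroups.

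Neither document contains a treatment-by-subgroup term, a posterior for the difference in effect between subgroups, or a shrinkage model. The responder regression in SAP 4.6.3 uses runcaciguat participants only, so it cannot supply a contrast of treatment effects.

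**The concern.** Whether one subpopulation responds better than another is a question about the difference between two treatment effects. Two separate within-subgroup analyses do not answer it. The posterior probability of superiority moves with subgroup size as well as with the effect. The probability that the runcaciguat rate exceeds 0.25 involves no placebo comparison, so a factor that is purely prognostic can shift it.

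A reader with two adjacent results, one above 0.9 and one below, will be inclined to see a selective responder. Protocol 2.1 says that runcaciguat itself will not be developed further and that the trial's value lies in more focused trials of a follow-up compound. A false lead from the subgroup tables would carry over into that programme. For renal function, the listed levels do not allow even an informal comparison.

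**Working it through.** **Inputs.** True response rates of 35% (runcaciguat) and 10% (placebo), and at least 40 evaluable per arm, from SAP 5 and Protocol 9.2. The two criteria and the prior are from SAP 4.2.2. Assumption for the check: the same true rates in every subgroup, so there is no effect modification at all.

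**Method.** Enumerate every pair of responder counts. Mark a pair as meeting PoC if P(π_ACT > π_PLC | data) ≥ 0.9 and P(π_ACT > 0.25 | data) ≥ 0.5 under the Beta(k+0.5, n−k+0.5) posteriors. Weight each pair by its binomial probability.

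**The plan's own figure.** At 40 per arm the probability of PoC is 0.903, which reproduces the stated 90% or more.

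**Subgroup sizes, same rates.** The probability of meeting both criteria is 0.500 at 10 per arm, 0.716 at 20 and 0.819 at 30.

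**Disagreement between two complementary subgroups** = p₁(1−p₂) + p₂(1−p₁).
- 20 and 20 per arm: 2 × 0.716 × 0.284 = 0.407. A simulation of 400,000 trials also gave 0.407, and among trials that meet PoC overall the figure is again 0.407.
- 10 and 30 per arm: 0.500 × 0.181 + 0.819 × 0.500 = 0.500.
- 15 and 25 per arm: 0.415.
- All 98 randomised participants, each half 26 v 23: 0.370.

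**Sensitivity to the uniform effect, halves of 20 per arm.**

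| Runcaciguat v placebo | P(both criteria) in a half | Halves disagree |
|---|---|---|
| 30% v 10% | 0.564 | 49.2% |
| 35% v 15% | 0.572 | 48.9% |
| 35% v 10% | 0.716 | 40.7% |
| 40% v 10% | 0.831 | 28.0% |
| 35% v 5% | 0.832 | 28.0% |
| 10% v 10% | 0.021 | 4.0% |

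**Dependence on size alone.** With identical observed rates of 30% v 10%, the posterior probability of superiority is 0.867 at 10 per arm, 0.945 at 20 and 0.975 at 30. The first misses 0.9; the other two pass.

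**Six factors together.** All six baseline factors re-divide the same participants. Simulating six independent random 20/20 splits of the same 40 + 40 participants gives at least one discordant pair in about 76% of trials (75% to 76% across simulation runs).

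**What the contrast would look like.** In the same setting, the posterior of the difference between the two subgroup treatment differences has a median 95% credible interval about 0.67 wide.

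**The case against.** The strongest reply is that these analyses are optional, labelled hypothesis-building, and feed no decision rule. That is correct, and it limits the weight of the point. The primary analysis and the PoC decision are unaffected.

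A reader might infer that the SAP will declare PoC subgroup by subgroup. It does not say so. SAP 4.2.2 and 5 define PoC for the study, and 4.2.4 speaks only of assessing the effect within subgroups. The disagreement rates therefore apply only if someone reads the two criteria within subgroups. Repeating the primary analysis leaves that open, and nothing in the SAP rules it out.

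A reader might also infer that only posterior probabilities would be shown. That is too strong. Per-arm credible intervals come with the repeated analysis, and descriptive DRSS statistics are broken down by subgroup. These would show some of the uncertainty, but they are not a contrast.

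Multiplying up the single-factor rate, 1 − (1 − 0.407)⁶ = 0.96, is tempting and wrong. Independent splits of the same participants do not give independent outcomes, because every split shares the same totals. Even 76% assumes six equal splits. Only age is cut at its median, and a level below 10 per arm falls outside the size rule.

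Lastly, the contrast is no cure for false leads. With one uniform effect and six factors, a probability of at least 90% that one half has the larger effect arises for 21% of factors, and for at least one factor in 74% of trials. That objection stands and shapes the fix: lead with the interval, and set no threshold on the probability.

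**Conclusion.** The point holds as a mismatch between the stated aim and the method. SAP 4.2.4 wants to know where response is better, yet neither document estimates a difference in effect between subgroups, and the eGFR levels have no complement.

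If the criteria are read within subgroups, two equal halves of 20 per arm disagree in about 41% of trials with no heterogeneity at all. The range is 28% to 49% when either rate moves by 5 points, and 50% for a 10/30 split. It falls to about 4% when both arms respond at 10%. At least one discordant pair in six appears in about 76% of trials. These figures rest on the design rates, 40 evaluable per arm, a uniform effect and, for the last, six random equal splits.

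The documents do not support any reading in which this threatens the study-level PoC conclusion, or in which subgroup PoC verdicts are already planned. It is an inexpensive improvement to an exploratory analysis, worth making before unmasking.

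**What to change.** In SAP 4.2.4:

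1. For each complementary baseline factor whose two levels both meet the size rule, subtract the posterior draws of the two subgroup treatment differences. Report the median and 95% credible interval of that contrast.
2. If the probability that one subgroup has the larger effect is also given, label it exploratory and unadjusted across factors, with no decision threshold.
3. State that the 0.9 and 0.5 PoC criteria are not applied within subgroups.
4. Add eGFR > 60 as the complement of eGFR ≤ 60.

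The cost is small. SAP 4.2.2 already generates 100,000 draws per arm for each analysis, so this takes one subtraction per factor, a few lines of code and revised SAP wording. It needs no new data and leaves the primary analysis unchanged. The one downside is that the contrast intervals will be wide, which is a fair account of what 80 participants can show.
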